7.2.5 Menstrual Bleeding Pattern

At each RM+7 visit from randomisation to end-of-treatment / cycle 4, the site staff should inquire about the subject's immediate past menstrual period, including the start and stop dates (if available) of menstrual bleeding and the amount of menstrual flow. The amount of menstrual flow will be graded as none (no bleeding), mild (less than normal flow), moderate (normal flow) and heavy (more than normal flow).

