8.3.2 Menstrual Bleeding

Presence of abnormal menstrual bleeding (e.g. amenorrhea, oligomenorrhea and menorrhagia) will be assessed by menstrual pattern at each RM+7 visit from randomisation to end-of-treatment / cycle 4 as part of the secondary endpoints and therefore is not to be reported as an adverse event unless it fulfils the criteria for an SAE.

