3.1 Overall Trial Design

In this trial, quinagolide vaginal ring or placebo vaginal ring will be administered sequentially for four menstrual cycles, where a menstrual cycle is considered the period between day 7 after return of menses (RM+7) in a cycle until the following day 7 after return of menses of the next cycle. The RM+7 visits in this trial can be scheduled within the period of 6-10 days after return of menses (RM+6-10).

The trial consists of the following periods:

- 1) Screening: starting from the signing of informed consent to randomisation (≤ 3 cycles) and including a wash-out period (only applicable to subjects using some hormonal contraceptives) and a screening cycle (cycle -1, applicable to all subjects)
- 2) Treatment: double-blind, placebo-controlled treatment with quinagolide vaginal ring or placebo vaginal ring administered sequentially for four menstrual cycles (cycles 1, 2, 3 and 4)
- 3) Follow-up: about 1 month after end-of-treatment

Screening: Subjects should be screened for eligibility within approximately 4 months of randomisation. Subjects who are currently using some hormonal products (e.g. combined oral contraceptive pill, progestogen and levonorgestrel-releasing intrauterine device (IUD)) may be eligible for the trial if they have completed the wash-out period and have return of menses.. In this case, subjects need to sign the informed consent before they discontinue those products.

Discontinuation of the products should follow their labelling (e.g. completing the current cycle of contraceptives before discontinuation). Subjects who are not using exclusionary hormonal products can enter the screening cycle directly. Prescriptions of analgesics for pain management are allowed in this trial.

After having completed the wash-out period (if applicable) and having RM, subjects will attend the screening RM+7 visit to undergo initial screening assessments, including a MRI examination by a high resolution 3-tesla (3T) machine. Depending on facilities at sites, MRI may not necessarily be scheduled at the same screening visit, but it must be scheduled on a day without bleeding to avoid biases and to ensure the availability of the central MRI reading report prior to randomisation. The MRI at screening, used as baseline, should not be obtained more than 1 menstrual cycle before randomisation.

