4.6 Listing

The subjects screened but not randomized/allocated to treatment will be presented with the reason(s) for screen failure in a data listing.

Based on the combined FAS, subject disposition with respect to analysis sets will be listed by site, treatment and subject number, this listing will include information on in which subgroup the subject was allocated to at randomisation. Subjects who discontinued from the trial will be listed by site, treatment, and subject number including information on timing of and reason for discontinuation.

5 Protocol Deviations

Protocol deviations will be rated as either minor or major. Protocol deviations impacting the primary endpoint and thereby affecting the conclusions of the trial will be rated as major. Major protocol deviations will lead to exclusion of data from the per protocol (PP) analysis sets. Data will not be excluded from the data analysis in case of minor protocol deviations.

The list of major protocol deviations includes, but is not restricted to:

- Treatment received not in accordance with randomisation
- Non-compliance with investigational medicinal product (IMP) treatment regimen for >20% of days during the non-menstrual period. The non-menstrual period of each cycle (cycle 1 to 4) is defined as the period from stop date of menstrual bleeding (excluding the stop day) to start of menstrual bleeding (excluding the start date). For a given cycle the stop date is based on the menstrual bleeding pattern form obtained at the beginning of the cycle, and the start date of menstrual bleeding is based on the menstrual bleeding pattern form obtained at the end of the cycle. The calculation of non-compliance percent is based on the combined non-menstrual period for cycle 1 to 4. In case of missing information on start and/or stop dates, the entire cycle in question will be considered as non-menstrual.

Unforeseen deviations deemed to impact the primary endpoint of the trial may additionally be rated as major protocol deviations by the Ferring clinical team, with support from the Syneos team, on the basis of a blinded review of data before declaration of clean-file and lock of database.

The list of major protocol deviations will be detailed and documented in the clean file document prior to database lock.

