As an additional analysis the menstrual bleeding pattern will be investigated by analysing the number days with menstrual bleeding (calculated as the stop date of menstrual bleeding minus start day plus 1) for each of the four cycles under treatment and the length of the menstrual cycle (calculated as the difference between two consecutive start of menstrual bleeding dates) for each of the four cycles under treatment. The baseline values for these two variables will be the number of bleeding days and the length of the menstrual period of the last pre-treatment cycle, respectively. If the stop date of a menstrual bleeding is missing due to the subject still bleeding at the RM+7 visit, the visit date plus 1 is used for calculating the length of the bleeding period. If the start date of menstrual bleeding is missing due to the subject having delayed or skipped menstrual bleeding, both of the two length of menstrual cycles will be considered missing, and the length of the bleeding period will be set to 0. To summarise the occurrence of delayed or skipped menstrual bleeding descriptive tables summarising the number of delayed or skipped menstrual bleedings and the number of subjects that experience at least one delayed or skipped menstrual bleeding will be prepared.

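### Bleeds still ongoing at the RM+7 visit are right-censored but analysed as if they ended the next day, so any lengthening of bleeding beyond the visit is understated

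*SAP*

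**What the plan says.** - **Counting rule.** In SAP 9.3.4.3, bleeding days per cycle are "calculated as the stop date of menstrual bleeding minus start day plus 1". The section presents this as an additional analysis of the bleeding pattern, next to menstrual cycle length.
- **Substitution rule.** The same section adds that, when the stop date is missing because the woman is "still bleeding at the RM+7 visit, the visit date plus 1 is used for calculating the length of the bleeding period". The rule is confined to that reason for a missing date.
- **Visit timing.** SAP 3.1 and Protocol 3.1.2 place RM+7 visits 6 to 10 days after return of menses. Protocol 6.3 adds that, if menses are delayed or absent, a visit must still take place within 35 days of the last ring change.
- **Collection of dates.** Protocol 7.2.5 has staff ask at each RM+7 visit about the "immediate past menstrual period, including the start and stop dates (if available) of menstrual bleeding". SAP section 5, on compliance, takes the date from the form filled in at that visit: "For a given cycle the stop date is based on the menstrual bleeding pattern form obtained at the beginning of the cycle". The follow-up call (Protocol 6.4.1) covers adverse events, medications and reasons for resuming treatment, not bleeding dates.
- **Adverse events.** Under Protocol 8.3.2, abnormal menstrual bleeding "is not to be reported as an adverse event unless it fulfils the criteria for an SAE", because the menstrual pattern assessment is meant to cover it.
- **Main bleeding-pattern analysis.** SAP 9.3.4.1 models the first change in flow amount by proportional odds. It does not use duration.

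**The concern.** If a woman is still bleeding at the visit, all that is known is that her bleed lasted at least until that day. The duration is right-censored. The SAP turns it into an exact value fixed by the visit date, so a 14-day and a 21-day bleed seen on the same visit day receive the same number.

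The case is foreseeable: Protocol 5.1.1 provides for ring changes at these visits whether or not bleeding has stopped, and the SAP writes a rule for it. The effect on menstrual bleeding pattern is a stated secondary objective. Bleeding days are the only planned analysis of duration, and the adverse event tables will not fill the gap for non-serious bleeding. A long bleed of normal flow is graded moderate under Protocol 7.2.5, so the flow analysis need not show it either. A finding of no effect on bleeding length could then partly reflect when visits were booked.

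**Working it through.** The documents give no figure for this rule, so there is none to reproduce. The check is date arithmetic.

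**Inputs.** Days = stop − start + 1 (SAP 9.3.4.3). Substituted stop = visit + 1 (same section). Visit = start + k, with k = 6 to 10 (SAP 3.1).

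**Entered length of an ongoing bleed.** (start + k + 1) − start + 1 = k + 2.

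| Visit day k | Known minimum, visit day included (k + 1) | Entered (k + 2) | Shortfall, 14-day bleed | Shortfall, 21-day bleed |
|---|---|---|---|---|
| 6 | 7 | 8 | 6 | 13 |
| 7 | 8 | 9 | 5 | 12 |
| 8 | 9 | 10 | 4 | 11 |
| 9 | 10 | 11 | 3 | 10 |
| 10 | 11 | 12 | 2 | 9 |

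The 14- and 21-day lengths are illustrations, not figures from the documents. Two identical long bleeds can differ by 12 − 8 = 4 days through booking alone.

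**Variants.** If return of menses is counted as day 1, or if the final + 1 is not applied to the substituted date, the range is 7 to 11 days. If the 35-day rule brings the visit to 0 to 5 days after onset, k + 2 gives 2 to 7 days. A visit later than the window would give more than 12.

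**Direction.** A bleed ending the day after the visit is entered correctly. One that ended on the visit day but was marked as ongoing is entered one day too long. Every longer bleed is entered too short. The arm with more such bleeds loses more days, so the difference shrinks toward zero. A lengthening that ends before the visit, say from 4 to 6 days, is unaffected.

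**Illustrative size (all assumed).** Take 12 women per arm. All bleeds last 5 days, except that a share p of active-arm women bleed for 15 days. The true difference in means is p × (15 − 5). The analysed difference is p × (8 − 5) to p × (12 − 5).

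| p | True difference (days) | Analysed difference (days) |
|---|---|---|
| 1/12 | 0.83 | 0.25 to 0.58 |
| 2/12 | 1.67 | 0.50 to 1.17 |
| 4/12 | 3.33 | 1.00 to 2.33 |

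Whatever p is, 3/10 to 7/10 of the difference is lost in this scenario. The rest remains.

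**The case against.** The case for leaving the rule alone has several parts.

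- **Narrow scope.** The rule applies only when the stop date is missing because bleeding continues. A reader might infer that all bleeding durations are capped at 8 to 12 days. They are not: any recorded stop date is used as it stands. This objection stands.
- **The signal survives.** A reader might infer that prolonged bleeding cannot be seen at all. That goes too far. Women still bleeding receive the highest value possible for their visit day, and the illustration leaves a reduced but non-zero difference. What is lost is length beyond the visit.
- **Other records exist.** A reader might infer that a long bleed is recorded nowhere else. In fact flow is graded at each RM+7 visit and analysed, cycle length is analysed, delayed or skipped bleeds are tabulated, observed endpoints are listed (SAP 9.6), and serious bleeding is still reported. None of these analyses duration.
- **Limited weight.** The analysis is additional, on a secondary endpoint. The primary endpoint and its Hochberg procedure are untouched. This stands.
- **Low expected frequency.** Protocol 1.3 reports no change to the menstrual cycle in phase 1, and eligibility requires 24- to 35-day cycles and excludes recent undiagnosed abnormal bleeding. Long bleeds may be rare. The documents give no frequency, so the illustration shows a mechanism and not an expected bias.
- **Late timing.** SAP 3.1, 3.3 and 12 report a randomisation error found after the last patient's last visit. New data collection was therefore largely closed when this text was written, although some follow-up calls may have been pending (Protocol 14.3). This limits the remedy mainly to the analysis.

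**Conclusion.** The concern holds as a limited point. Bleeds ongoing at the visit are censored but analysed as observed, at 8 to 12 days for in-window visits under the literal formula. Length beyond the visit is lost, the value depends on scheduling, and any excess of bleeding beyond the visit in one arm is attenuated.

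This rests on two assumptions. Visit days are distributed similarly in the two arms; if not, scheduling could itself create a difference. Sites also did not fill in stop dates afterwards. Neither document describes such a step, but if it happened, the date is no longer missing and the rule does not apply. How large the effect is depends on how many bleeds were ongoing at the visit, and no planned table reports that number.

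**What to change.** In SAP 9.3.4.3, before unblinding:

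1. State that any recorded stop date is used, including one entered after the visit.
2. Flag each visit-plus-1 value as right-censored, including any that supplies the baseline.
3. Tabulate by arm and cycle the number and percentage of bleeds ongoing at the visit.
4. Add a sensitivity analysis of bleeding days that respects censoring, for example time from start to stop of bleeding, censored at the visit. It cannot recover the missing length, but it stops treating the visit as the end of the bleed.

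These steps use dates and bleeding status that the rule already requires, so the cost is SAP wording, one table and one analysis.

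Where contacts remain, or in a later trial, have sites record the actual stop date of an ongoing bleed at the next RM+7 visit, or at the follow-up call after visit 8. That is one question at a contact that already takes place. The downside is about one month of recall.

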6.2 Screening

Potential participants will be scheduled to come to the clinic for the screening assessments. The screening period should not exceed 5 months. A menstrual cycle in this trial is considered the period between RM+7 in a cycle until the following RM+7 in the next cycle. The RM+7 visit can be scheduled 6-10 days after return of menses (RM+6-10).

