6.3 Treatment Period

If subjects do not have menstrual bleeding or have delayed menstrual bleeding in a cycle during the treatment period, a visit must be arranged within 35 days of the last ring replacement visit.

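### The cycle-length analysis discards cycles whose next menses has not started by the visit, which biases it towards no lengthening if treatment causes skipped or very late menses

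*SAP*

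**What the plan says.** Change in menstrual bleeding pattern is a secondary endpoint. SAP 9.3.4.3 adds to it: "As an additional analysis the menstrual bleeding pattern will be investigated by analysing the number days with menstrual bleeding" and the cycle length, the latter "calculated as the difference between two consecutive start of menstrual bleeding dates", for each of the four treated cycles. SAP Table 9-1 assigns the endpoint to repeated measures ANCOVA as well as to a proportional odds model.

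The rule at issue begins "If the start date of menstrual bleeding is missing due to the subject having delayed or skipped menstrual bleeding". In that case "both of the two length of menstrual cycles will be considered missing, and the length of the bleeding period will be set to 0". The SAP then plans "descriptive tables summarising the number of delayed or skipped menstrual bleedings" and of subjects with at least one such event, with no between-arm test or estimate stated.

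SAP 9.3.4 plans no imputation for these endpoints, and SAP 9.3 plans no sensitivity analysis for any secondary endpoint. When menses are late or absent during treatment, Protocol 6.3 says that "a visit must be arranged within 35 days of the last ring replacement visit". Protocol 6.2 allows the ring visit 6 to 10 days after return of menses.

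**The concern.** A repeated measures ANCOVA handles data that are missing at random. Here a length goes missing because the next menses had not come by the visit, so missingness depends on the unobserved value. Cycles that end before the visit stay in the model and those that do not are removed. If treatment makes some menses skip or come very late, the cycles carrying that effect are the ones removed.

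The stakes are limited but real. Effect on bleeding pattern is a stated secondary objective. Protocol 8.3.2 keeps amenorrhoea and oligomenorrhoea out of adverse event reporting unless serious, because this endpoint is meant to capture them. Protocol 1.2 and 1.3 report no effect on the cycle in phase 1. A null cycle-length estimate here could be read as confirming that, when part of it comes from the missing-data rule.

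**Working it through.** The documents give no delay rate, standard deviation or power for cycle length, so there is no planned figure to reproduce. All delay rates and cycle distributions below are assumptions.

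**1. When the rule applies.** Latest visit day after the previous start = day of ring visit + 35.
- Ring visit at day 6: 6 + 35 = 41
- Ring visit at day 10: 10 + 35 = 45

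With the visit at its limit, a 38-day cycle, already outside the 24 to 35 day entry range (Protocol 4.1.1), has a recorded start and is kept. An earlier visit moves the cutoff earlier.

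**2. Share of lengths lost.** Four treated lengths use five start dates, recorded at visits 2, 5, 6, 7 and 8. The first belongs to a pre-treatment menses and is taken as recorded. Suppose each of the other four is unrecorded with probability 0.20, independently.
- Cycle 1 (one start at risk): 20% lost
- Cycles 2 to 4 (two starts at risk): 1 − 0.8 × 0.8 = 36% lost
- Average: (20 + 3 × 36) / 4 = 32%

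**3. Effect on the mean.** Suppose usual cycles last 29 days, 20% of active-arm cycles last 44 to 52 days, and placebo has no delays.
- True difference: 0.2 × (44 − 29) = 3.0 days, up to 0.2 × (52 − 29) = 4.6 days
- After the rule: the remaining cycles average 29 in both arms, so the difference is near 0

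The lower figure needs the visit before day 44. With a ring visit at day 10 and the next visit at day 45, a 44-day cycle would be recorded and kept.

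**4. Simulation with a placebo rate and a cutoff.** Usual cycles have mean 29 and SD 3 days, with 400,000 cycles per arm. Cells are the active minus placebo difference in mean length, in days.

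| Scenario | All cycles kept | Rule, cutoff day 41 to 45 | Rule, cutoff day 36 |
|---|---|---|---|
| Cycles of 43–60 days: 2% placebo, 10% active | 1.8 | 0.0 to 0.2 | 0.0 |
| Cycles of 43–60 days: 2% placebo, 20% active | 4.0 to 4.1 | 0.0 to 0.4 | 0.0 |
| Cycles of 36–60 days: 2% placebo, 10% active | 1.5 | 0.2 to 0.4 | 0.0 |
| Cycles of 36–60 days: 2% placebo, 20% active | 3.4 | 0.4 to 0.9 | 0.0 |
| All active cycles 3 days longer | 3.0 | 3.0 | 2.5 |
| All active cycles 6 days longer | 6.0 | 5.8 to 6.0 | 4.3 |

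This compares simple means of one cycle per subject. It does not fit the repeated measures model or include the loss of the second adjacent length.

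**5. Bleeding days.** A delayed bleed that comes after the visit scores 0 in one cycle and may be counted at its real duration in the next. If a usual bleed lasts 5 days (assumption), zeros in 10% to 20% of active-arm cycles lower the mean by 0.10 × 5 = 0.5 to 0.20 × 5 = 1.0 day, although no bleed was shorter.

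**The case against.** The strongest reply is that the rule is narrow and the signal survives elsewhere. It needs a missing start date, so a late menses that starts before the visit is kept, and the table shows a general lengthening of 3 or 6 days almost fully preserved at the day 41 to 45 cutoff. Skipped and delayed bleeds are tabulated by event and by subject. The flow analysis in SAP 9.3.4.1 is tested, and the flow scale in Protocol 7.2.5 has a grade for no bleeding, so an absent bleed can count as a change. Scoring 0 days keeps the event in the bleeding-days model. The rates used above are chosen, not documented.

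All of this stands, and it limits the point without removing it. The tables carry no stated comparison. The flow analysis concerns amount and does not say how a delayed bleed is graded. Neither gives an estimate of cycle length.

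A reader might also object to the rule for ongoing bleeding, under which "the visit date plus 1 is used for calculating the length of the bleeding period". With stop minus start plus 1, the same ongoing bleed scores 6 + 1 + 1 = 8 days if seen at day 6 and 10 + 1 + 1 = 12 if seen at day 10. That adds noise, but the rule is the same in both blinded arms and nothing in the documents points to a between-arm bias.

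**Conclusion.** The point holds in a limited form. Cycles with no menses by the visit are missing because of their length, so the planned between-arm estimate of cycle length is biased towards no lengthening when an effect acts through skipped or very late menses. Under the assumed 20% rate with independent delays, about 32% of active-arm lengths go and a difference of roughly 3 to 4.6 days can shrink to near 0. The direction follows from the rule; the size rests on assumed rates and on how early the visit is held.

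A reader might infer that every delayed cycle is deleted, or that the trial would hide a menstrual effect. The documents support neither: delays with a recorded start are kept, and the events are tabulated. This is an additional analysis of a secondary endpoint, and the primary endpoint is unaffected.

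**What to change.** In SAP 9.3.4.3:

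- **Cycle length.** When a later visit records the next start date, compute the interval from the previous start to it. Protocol 7.2.5 already has sites ask about the immediate past period at each such visit. State how an interval spanning a skipped menses is labelled. Otherwise, treat the cycle as right-censored at the visit date. This includes the last cycle, because the follow-up call (Protocol 6.4.1) is not planned to collect menses dates.
- **Comparison.** Compare time to next menses between arms with a time-to-event model that accounts for repeated cycles per subject.
- **Delayed or skipped bleeds.** Report the proportion of subjects with at least one, by arm, with a confidence interval for the difference.
- **Bleeding days.** Keep 0 only where no bleed occurred, so far as the records show. Where a later visit records the delayed bleed, use its duration once instead of scoring 0. Setting such cycles to missing would bring back missingness that depends on the outcome.

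The cost is revised SAP wording and one extra model. No new data are needed.

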9.4 Pharmacokinetics

Plasma concentration of quinagolide and its metabolites will be analysed descriptively, by summarising (N, mean (SD), geometric mean (CV%), min, and max) by visit, for all subjects that received active quinagolide. A population pharmacokinetic modelling method will be outlined in a

modelling analysis plan under the responsibility of the Translational Medicine Department of Ferring Pharmaceuticals A/S and the results will be reported separately.

